5.1.3 Cognitive and Neurodevelopment

5.1.3.1 Ohio State University (OSU) Autism Rating Scale

A MMRM model will be fitted to the change from baseline to weeks [redacted] and [redacted] in the OSU autism rating scale total impairment mean. The model will be fitted and results presented as described in section 5.1.1.1.

The observed OSU autism rating scale social interaction impairment mean, communication impairment mean, restricted patterns mean and total impairment mean and corresponding change from baseline will be summarised over time. In addition, the observed means at [redacted] and [redacted] and the change from [redacted] to [redacted] will also be summarised.

The OSU autism rating scale data will be listed.

5.1.3.2 OSU CGI-S and CGI-I

The OSU CGI-S and CGI-I will be analysed and summarised as described in section 5.1.2.1. The MMRM analysis of OSU CGI-I results will be fitted to the observed

values at weeks [] and []. A compound symmetry covariance matrix will be used for the repeated visits within subject. The by subject line plot of OSU CGI-I results will include [] and [].

The OSU CGI-S and CGI-I data will be listed.

5.1.3.3 Peabody Picture Vocabulary Test

An ANCOVA will be fitted to the change from baseline to end of treatment in the Peabody picture vocabulary test age-based standard score. The model will be fitted and results presented as described in section 5.1.2.1 for CGI-S.

The observed raw score, age-based standard score, percentile rank and age equivalent in years and corresponding change from baseline over time will be summarised. In addition, the above scores at [] and [] and change from [] to [] will also be summarised. The above Peabody picture vocabulary test endpoints (apart from the age equivalent (years) endpoint) will also be presented over time (V2, [] and []) using by subject line plots by dose group. In addition, line plots will present the adjusted LS mean changes from baseline to end of treatment and SEs, as estimated by the ANCOVA, by dose group for the Peabody picture vocabulary test age-based standard score. Raw mean changes from [] to [] will be presented on the same plot.

The Peabody picture vocabulary test data will be listed.

5.1.4 Biomarker

5.1.4.1 Dual-energy X-ray Absorptiometry (DXA) Whole Body Scan of Lean Muscle Mass

An ANCOVA will be fitted to the change from baseline to end of treatment in the DXA scan total lean muscle mass (g). The model will be fitted and results presented as described in section 5.1.2.1 for CGI-S.

The observed muscle mass and corresponding change from baseline to end of treatment will be summarised separately for the arms, the legs and the total muscle mass. The observed muscle mass for the arms, the legs and total muscle mass will also be presented over time ([] and []) using by subject line plots by dose group. In addition, line plots will present the adjusted LS mean changes from baseline to end of treatment and SEs, as estimated by the ANCOVA, by dose group for the DXA scan total lean muscle mass (g).

Lean muscle mass data will be listed.

5.1.4.2 []

[]
[] . []
[]

5.2 Handling of Missing Data

There is no requirement for imputation of missing data in the MMRM models detailed in section 5.1, since the MMRM models handle missing data by assuming that missing data is missing at random (MAR), so that mean changes from baseline are estimated assuming that subjects with missing data will perform in the same way as

subjects with the same baseline covariate values and the same observed data so far.

In the ANCOVA models, if a subject has missing data at week █ the subject will be excluded from the analysis and so will be assumed to be missing completely at random (MCAR).

Prior to database lock, the data will be reviewed to assess whether any subjects were unable to complete an assessment due to "extreme" factors affecting their ability to complete an assessment e.g. due to a serious deterioration in their physical state. In the event that such subjects are identified, appropriate methods for handling this specific type of missing data will be used.

For example, in the event that some fraction q of the subjects become non-ambulatory, the results for this analysis can then be scaled to reflect the proportion of non-ambulatory subjects. For example, suppose, for a given endpoint within $N=8$, $q=2/8 = 25\%$ of the subjects were non ambulatory at █ weeks. Suppose the mean change from baseline at █ weeks in the 6/8 who were ambulatory is \bar{x} with estimated SE s , then the scaled result allowing for the non ambulatory subjects is then $\bar{x}/(1 - q) = \bar{x}/(1 - 0.25)$. The log scale SE of this scaled result can then be estimated as $\sqrt{\frac{s^2}{\bar{x}^2} + \frac{q}{N(1-q)}}$.

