### 8.2 Secondary endpoints

Secondary endpoints will include the following:

- Blood pharmacokinetics (PK) of tideglusib
- 10 metre walk/run test (self-selected and fastest velocity)
- Computerised handgrip myometer measure of grip strength and muscle relaxation time
- Respiratory Forced vital capacity (FVC)
- Clinical Global Impressions– Severity and –Improvement (CGI-S and CGI-I)
- Actigraphy (measure daily averages of: number of bouts of activity, number of steps taken and energy expenditure)
- Nine Hole Peg Test (NHPT)
- Dual-energy X-ray absorptiometry (DXA) whole body scan of lean muscle mass (g) legs, arms, and total
- Top 3 Concerns VAS (caregiver-completed and where possible, subject-completed also)
- OSU Autism Rating Scale (OARS)
- OSU Autism CGI
- Clinician-completed Domain Specific Cause for Concern VAS: Myotonic Dystrophy
- Peabody Picture Vocabulary Test
- [REDACTED] levels and activity

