### **Assessment of Muscle Functioning**

#### **10.2.1 10 metre walk/run test**

The 10 metre walk/run test is a performance measure used to assess walking speed in metres per second over a short distance. It can be used as an assessment of functional mobility. The test will be conducted according to the schedule of assessments (Table 1) and will be performed at the subject's preferred walking speed and then at the fastest speed possible. For each speed, 3 assessments will be completed with a rest period until the subject has recovered.

The subject walks without assistance for 12 metres while the time taken to walk from metre 1 to meter 11 is recorded. The timing starts and stops when the toes of the leading foot cross the 1 and 11 metre marks respectively. If assistive devices are needed, these can be used but must be documented and kept consistent for that subject throughout the study.

For the fastest speed possible, the assessor will document whether the subject was able to run, walk fast or walk for each assessment. Whether the subject is running is defined as both feet being off the floor at the same time. If the subject is not able/willing to perform the fastest speed possible for all 3 assessments, this will also be recorded.

Appendix A provides further information on the test including verbal instructions to give to the subject.

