5.1.1 Muscle Function

5.1.1.1 10 Metre Walk/Run Test

In the event that a subject does not complete a walk/run test, then that test result will not be included in derivation of the observed mean of the repeat assessments, which will use only "valid" results where the subject completed the assessment. A "valid" result will be any non-missing result where the recorded distance covered is not <10 metres. Where the distance is <10 metres, the test result will be assumed missing.

A MMRM will be fitted to the change from baseline to weeks █ and █ in the time taken (seconds) to complete the 10 metre walk/run test at the preferred speed (calculated for each visit as the mean of the repeat assessments). The model will include the baseline value as a covariate, dose group, and visit as fixed effects, and

the treatment-by-visit interaction. F-tests from PROC MIXED will be based on Kenward-Roger's adjusted degrees of freedom. A compound symmetry covariance matrix will be used for the repeated visits within subject.

Adjusted LS Means for the dose group means at each visit estimated by the above model will be presented, together with the associated SE, 95% CIs and 2-sided p-values.

The observed mean (of the repeat assessments at a visit) for the time taken (seconds) to complete the 10 metre walk/run test and the change from baseline will be summarised over time separately for the preferred speed and the fastest speed. The observed mean at the start of the [REDACTED] run-in [REDACTED] and at baseline (■) and the change from ■ to ■ in the observed mean will also be summarised separately for the preferred speed and the fastest speed.

The observed mean (of the repeat assessments at a visit) in the time taken (seconds) to complete the 10 metre walk/run test will be presented using by subject line plots over time (■, ■ ■ and ■) by dose group separately for the preferred speed and the fastest speed. In addition, line plots will present the adjusted LS mean changes from baseline and SEs over time, as estimated by the MMRM model, by dose group for the time taken (seconds) to complete the 10 metre walk/run test at the preferred speed. Raw mean changes from ■ to ■ will be presented on the same plot.

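### The method written out for loss of ambulation divides a mean change by (1 − q), so when the remaining walkers improve, losing more walkers makes the reported improvement larger

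*SAP*

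**What the plan says.** SAP 5.2 has the data looked at before database lock for subjects who missed an assessment for extreme reasons, such as serious physical decline. The commitment that follows is general: "In the event that such subjects are identified, appropriate methods for handling this specific type of missing data will be used". One example is then given. If a fraction q become non-ambulatory, "the results for this analysis can then be scaled to reflect the proportion of non-ambulatory subjects". The example takes N = 8 and q = 2/8 = 25%. With x̄ the mean change from baseline in the six who still walk and s its standard error, "then the scaled result allowing for the non ambulatory subjects is then" x̄/(1 − q) = x̄/(1 − 0.25). It continues: "The log scale SE of this scaled result can then be estimated as" √(s²/x̄² + q/(N(1 − q))). Nothing restricts the sign or size of x̄, and the example is not tied to one endpoint.

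For the walk test, SAP 5.1.1.1 models the change from baseline "in the time taken (seconds) to complete the 10 metre walk/run test at the preferred speed", so a negative change is an improvement. The same section treats a walk that stops short of 10 metres as missing, and 5.2 leaves missing values in the repeated-measures models to a missing-at-random assumption. Protocol 10.2.1 describes the test differently: "The 10 metre walk/run test is a performance measure used to assess walking speed in metres per second over a short distance". Protocol 8.2 likewise lists velocity as the secondary endpoint.

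**The concern.** All subjects must be able to walk at entry, so a subject who stops walking has deteriorated. The 5.2 provision is the SAP's only stated protection against treating that loss as ignorable missing data. A sound method would make the group result worse when it happens. Dividing a change score by a number below 1 instead amplifies whatever the remaining walkers did: an improvement grows, a worsening grows, and a mean change of zero stays zero however many are lost. The log-scale standard error has a related fault, because a change can be negative or zero and a logarithm cannot accommodate that.

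With 8 subjects per dose group, one or two losses are enough to alter the reported effect. The sponsor and the site also know the treatment (Protocol 9.3), so a method chosen at the pre-lock review, with this example as the only guide, is open to data-dependent choice.

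**Working it through.** **Inputs.** From SAP 5.2: N = 8, q = 2/8, the scaling x̄/(1 − q) and the standard-error formula. From SAP 5.1.1.1: the walk variable is change in seconds. From SAP 2.4: 8 subjects per dose group. The documents give no values for x̄, s or walking speed; those below are assumptions.

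**1. The SAP's own figures.** 1/(1 − 0.25) = 1.333 and q/(N(1 − q)) = 0.25/(8 × 0.75) = 0.0417. By the delta method, Var[log(1 − q̂)] = [q(1 − q)/N]/(1 − q)² = q/(N(1 − q)), and Var[log x̄] = s²/x̄². The SAP's expression is therefore the delta-method standard error of log{x̄/(1 − q)}. The algebra is right; the question is what it is applied to.

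**2. Effect on the estimate.** If the scaled result is read as a mean over all N subjects, the change c credited to each lost walker solves (1 − q)x̄ + qc = x̄/(1 − q), so c = x̄(2 − q)/(1 − q). If lost walkers are instead scored 0 m/s, the group's mean change in speed is (1 − q)g − q·v, where g is the walkers' mean gain and v is the lost subjects' mean baseline speed. That is negative unless g exceeds q/(1 − q) of v.

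| Lost of 8 | Multiplier 1/(1 − q) | −1.0 s is reported as | Credit per lost walker, (2 − q)/(1 − q) | Gain needed to avoid net worsening at 0 m/s, q/(1 − q) |
|---|---|---|---|---|
| 1 | 1.14 | −1.14 s | 2.14 x̄ | 14% of v |
| 2 | 1.33 | −1.33 s | 2.33 x̄ | 33% of v |
| 3 | 1.60 | −1.60 s | 2.60 x̄ | 60% of v |
| 4 | 2.00 | −2.00 s | 3.00 x̄ | 100% of v |

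**3. Level against change.** Assume all 8 start at 10 s, two stop walking and six reach 9 s.
- Scaling the level: 9/0.75 = 12 s. This equals counting non-walkers as speed zero: 0.75 × 10/9 = 0.833 m/s, and 10/0.833 = 12 s. The group has worsened by 2.0 s.
- Scaling the change, as the SAP does: −1.0/0.75 = −1.33 s, an improvement.

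The same contrast in speed, with q = 2/8, an assumed baseline of 0.5 to 1.6 m/s for everyone and a 10% gain in walkers:
- SAP scaling: 0.05/0.75 = +0.07 to 0.16/0.75 = +0.21 m/s.
- Lost walkers at 0 m/s: 0.75 × 0.05 − 0.25 × 0.5 = −0.09 to 0.75 × 0.16 − 0.25 × 1.6 = −0.28 m/s.

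**4. The interval.** Take q = 2/8, x̄ = 0.4 and s = 0.4 (assumed). The log standard error is √(1 + 0.0417) = 1.021 and the scaled estimate is 0.4/0.75 = 0.533. Back-transforming, 0.533 × exp(±1.96 × 1.021) gives 0.07 to 3.94. The unscaled interval, 0.4 ± 1.96 × 0.4, is −0.38 to 1.18. An exponentiated interval cannot include zero whatever the data. At x̄ = −0.4 the logarithm does not exist, although the formula still returns a number because x̄ is squared.

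**5. Significance.** At x̄ = −1, s = 0.4, q = 0.25, the formula gives √(0.16 + 0.0417) = 0.449. On the linear scale that is 0.449 × 1.333 = 0.599. The ratio of estimate to standard error moves from 1/0.4 = 2.50 to 1.333/0.599 = 2.23, so it falls.

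**The case against.** The strongest reply is that the scaling is only an example of what can be done; the commitment is to the review and to suitable methods. The perverse result needs three things together: walkers are lost, this example is used, and the remaining walkers improve on average. If they worsen, enlarging the worsening is the plausible direction. Treatment lasts 12 weeks in subjects who walk at entry, and the documents give no expected rate of loss. All of this is true and limits how often the fault would bite. It does not make the only written method sound.

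On the interval, the SAP gives a standard error and never says that an interval will be formed by exponentiating. One could work with log|x̄|, which at x̄ = −0.4 mirrors the interval to −3.94 to −0.07. That is fair, but the mirrored interval cannot include zero either.

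The speeds in the m/s illustration are assumed, and the SAP does not model speed. The credit per lost walker also depends on reading the scaled result as an all-subject mean. Neither is needed for the conclusion: the multipliers depend on q alone.

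A smaller repair would apply the same formulas to mean walk time. Step 3 shows that this puts the estimate in the right direction. However, the SAP's analysis is of change, and a comparison with baseline would also need the covariance with baseline times, which the formula lacks.

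Finally, a significant worsening of ambulation is to be recorded as an adverse event (Protocol 10.4.5), and walk data are listed by subject. The loss would be visible, but that does not correct the efficacy estimate.

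**Conclusion.** The concern holds. Followed as written, the example reports a larger improvement the more subjects stop walking, provided the others improve on average: 14% larger for one of 8 and 33% larger for the SAP's own two of 8. This rests only on the SAP's formula and the sign of x̄. The log-scale standard error does not suit a change score: the logarithm is undefined in the direction of benefit for walk time, and a back-transformed interval can never include zero. The formulas are correct for a positive level; the error is in applying them to a change. The damage is to effect size and interval rather than to the p-value. It concerns secondary efficacy endpoints and arises only if the contingency occurs. It should be fixed before database lock but does not threaten the primary safety objective.

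**What to change.** Delete the x̄/(1 − q) scaling and its log-scale standard error from SAP 5.2. Keep the pre-lock review, and specify before database lock a method in which loss of ambulation counts as a bad outcome. Either of these would do:

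- **Worst rank.** A sensitivity analysis in which walk assessments missed because of deterioration rank below every completed one. The SAP should name the test and the comparison. Because 5.2 covers any assessment, it should also say which other endpoints the rule applies to.
- **Velocity.** Analyse the 10 metre test as 10 m divided by the recorded seconds, which is the protocol's named endpoint, with 0 m/s where the subject cannot walk because of deterioration. SAP 5.1.1.1 then needs an exception to its rule that a walk short of 10 metres is missing.

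The cost is SAP wording and modest programming. The velocity option is the larger change, since the walk-test model, summaries and plots would follow the new variable. Both options use times already recorded. Both also need the reason for non-completion: Protocol 10.2.1 asks for a note of inability or unwillingness only at the fastest speed and does not separate the two, so for the preferred-speed endpoint the pre-lock review must establish and document the reason. The other consequence is a less favourable efficacy estimate if walkers are lost, which is the intended behaviour.

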6 PHARMACOKINETICS

The details of any blood concentration/pharmacokinetic analyses will be described in a separate PK analysis plan.

7 SAFETY EVALUATION

7.1 Adverse Events

Adverse events will be coded using the latest MedDRA dictionary version.

A NTEAE is defined as an AE that started on or after the administration of placebo treatment but before the start of the administration of active treatment.

A TEAE is defined as an AE that started on or after the start of the administration of active treatment. If adverse event dates are incomplete and it is not clear whether the adverse event was treatment-emergent, it will be assumed to be treatment-emergent.

A "treatment period" TEAE is defined as an AE that started on or after the start of active treatment but before 2 days after active treatment was discontinued. A "post treatment period" TEAE is defined as an adverse event that started from 2 days after the active treatment was discontinued.

Adverse events of special interest (AESIs) are recorded if it is identified from a review of the haematology and biochemistry results that the subject has clinically significant liver function test elevation.

The following summaries of the total number of “treatment period” TEAEs, “post treatment period” TEAEs and all TEAEs (both “treatment period” and “post treatment period” TEAEs) will be provided at the event and subject levels as indicated:

- TEAEs (events and subjects).
- TEAEs by relationship to active treatment (events and subjects).
- TEAEs by severity (mild/moderate/severe) (events and subjects).
- Serious TEAEs (events and subjects).
- Serious active treatment related TEAEs (events and subjects).
- TEAEs leading to withdrawal (subjects only).
- TEAEs leading to discontinuation of active treatment (subjects only).
- Active treatment related TEAEs leading to discontinuation of active treatment (subjects only).
- TEAEs leading to death (subjects only).

The following summaries of NTEAEs will be provided at the event and subject levels as indicated:

- NTEAEs (events and subjects).
- NTEAEs by severity (mild/moderate/severe) (events and subjects).
- Serious NTEAEs (events and subjects).
- NTEAEs leading to withdrawal (subjects only).
- NTEAEs leading to death (subjects only).

In the above summaries, if a subject experienced more than one NTEAE/TEAE, the subject will be counted once using the most related event for the “by relationship to active treatment” summary and at the worst severity for the “by severity” summary.

The number and percentage of subjects experiencing “treatment period” TEAEs, “post treatment period” TEAEs and all TEAEs will be presented by:

1. System Organ Class (SOC) and Preferred Term (PT).
2. PT.
3. SOC, PT and severity.
4. SOC, PT and relationship (related/unrelated) to active treatment.

In addition, the number and percentage of subjects experiencing NTEAEs will be presented by:

1. SOC and PT.
2. SOC, PT and severity.

For all the above, SOC and PT will be presented in decreasing frequency of the total number of subjects with NTEAEs/TEAEs.

Further details of the above four tables are given below:

1. If a subject experienced more than one NTEAE/TEAE, the subject will be counted once for each SOC and once for each PT.

2. If a subject experienced more than one TEAE, the subject will be counted once for each PT.
3. If a subject experienced more than one NTAE/TEAE, the subject will be counted once for each SOC and once for each PT at the worst severity.
4. If a subject experienced more than one TEAE, the subject will be counted once for each SOC and once for each PT using the most related event.

Adverse event data will be listed in full and this will also include a treatment emergent flag, a treatment period TEAE flag, a post treatment period TEAE flag, a flag for AESIs, the time of onset of event relative to first dosing of active treatment, and duration of AE.

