**9. STUDY MEDICATION AND ADMINISTRATION**

**9.1 Study medication**

Investigational Medicinal Product: Tideglusib

**Chemical Name:** 4-benzyl-2-naphthalen-1-yl-1,2,4-thiadiazolidine-3,5-dione

The Investigational Medicinal Product is a powder for oral suspension designated as formulation F06-037F. This powder is filled into sachets containing one dose of powder of either [REDACTED] or [REDACTED]. The content of the sachets must be [REDACTED]

A similar formulation to F06-037F has been developed to be used as placebo according to protocol and study design. The placebo drug product (coded F07-101) is supplied in the same type of units containing sachets of the same strength as the active product. It is a powder for oral suspension in [REDACTED]  
[REDACTED]

The single dose sachets should be stored in refrigerated conditions [REDACTED] prior to reconstitution. Shelf life periods may be extended if justified by stability results and use-by-dates will be modified on the packaging. Sponsor approval must be sought prior to re-labelling.

The single-blind IMP will be provided to the subject and their caregiver at each visit [REDACTED]

IMP (either active tideglusib or matched placebo) will be packaged in cartons of 18 sachets. With 18 sachets per carton, there is sufficient medication to cover a [REDACTED]

[REDACTED] An additional 2 sachets of medication are also included in the carton in the event that during the process of opening the sachets, medication is inadvertently lost. In this event, the subject/caregiver will be instructed not to use the sachet from which drug has been lost, but to open a new replacement sachet from the same carton so that the full dose can be given.

Each sachet and carton will be externally labelled with a medication ID number, expiry date and clinical trial information. The IMP (sachets and cartons) will be labelled according to Annex 13, Volume 4 of EUDRALEX and will be in accordance with all other applicable regulatory requirements.

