**9.1.2 Subjects in Cohort 2 will receive the following cartons of medication:**

Run-in Phase (dispensed at [REDACTED])

1 x carton containing 18 sachets [REDACTED]

Active Phase (dispensed at [REDACTED])

1 x carton containing 18 sachets [REDACTED]

The caregiver will be given clear instructions that all unused and used sachets should be returned at each visit and they will be provided with new medication at the subsequent visit. If IMP is not returned at a visit, the caregiver must be informed to only use sachets from the new carton(s) and return both sets of IMP at the next visit.

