## **10.2.12 Peabody Picture Vocabulary Test**

The PPVT-4 scale is a norm-referenced instrument for measuring the receptive (hearing) vocabulary of children and adults. It contains training items and 228 test items, each consisting of four full-colour pictures as response options on a page. For each item, the examiner says a word, and the examinee responds by selecting the picture that best illustrates that word's meaning.

Each administration of the test produces a raw score as well as a standard score, derived from the number of responses attempted and the number of correct responses. The percent of correct responses is also reported.

The test will be performed at Run-in [REDACTED] Baseline [REDACTED] and End-of-Treatment [REDACTED] to compare scores prior and after single-blind placebo and single-blind tideglusib respectively.

10.2.13

Details on collection, handling, storage, processing and shipment of the [REDACTED] sample will be provided in a separate laboratory manual.

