### **11.4 Statistical Methods for Safety**

All safety summaries and analyses will be performed using the SAF.

All AEs will be coded using the MedDRA dictionary and will be summarised by treatment using frequencies and percentages as appropriate.

Other safety data, including laboratory, vital signs and ECG values including change from baseline will be summarised. Changes in safety parameters from baseline [REDACTED] over time will be described by treatment dose, and shift tables at time points of interest will be generated. Changes from the start of the [REDACTED] run-in period [REDACTED] to baseline [REDACTED] will also be produced as indicative of the effect of [REDACTED] of [REDACTED] treatment.

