4.4 Administration of Investigational Product

Percentage compliance with administration of active treatment will be summarised (see section 4.2 for the derivation).

The following active treatment exposure summaries will also be provided: total amount (mg) of active treatment taken (see section 4.2 for derivation) and the number of days of exposure to the active treatment derived from the subject diary card data as follows:

(Date of [REDACTED] of [REDACTED] of active treatment – date of [REDACTED] of [REDACTED] of active treatment + 1) + (Date of [REDACTED] of [REDACTED] of active treatment – date of [REDACTED] of [REDACTED] of active treatment + 1), where the [REDACTED] duration is only applicable to subjects who are [REDACTED]

In addition, the following active treatment exposure summaries will be provided for Cohort 1 subjects:

- the number of days of exposure to [REDACTED] tideglusib for all Cohort 1 subjects and separately for Cohort 1 subjects who are [REDACTED] from [REDACTED] tideglusib defined as:

Date of [REDACTED] of [REDACTED] of active treatment – date of [REDACTED] of [REDACTED] of active treatment + 1.

- the number of days of exposure to [REDACTED] tideglusib for subjects who are [REDACTED] from [REDACTED] tideglusib defined as:

Date of [REDACTED] of [REDACTED] of active treatment – date of [REDACTED] of [REDACTED] of active treatment + 1.

- the number of subjects that were [REDACTED]

[REDACTED] dose, the additional variables outlined above for Cohort 1 will be derived for both Cohorts.

The above derived variables and study drug dispensing, study drug return, study drug down titration and subject diary card information will be listed.

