- Figure 14.2.3.1_AH1a Bar Chart of Pulmonary Function Test over Time – Mean Value +/- Standard Deviation
- Figure 14.2.3.1_AH1b Scatter Plot of Pulmonary Function Test at Week █
- Figure 14.2.5.1_AH1a Bar Chart of Time Taken (Seconds) to Complete the Nine Hole Peg Test over Time – Mean Value +/- Standard Deviation
- Figure 14.2.5.1_AH1b Scatter Plot of Time Taken (Seconds) to Complete the Nine Hole Peg Test at Week █
- Figure 14.2.6.1_AH1a Bar Chart of Clinical Global Impression over Time – Mean Score +/- Standard Deviation
- Figure 14.2.6.1_AH1b Bar Chart of Percentage of Subjects with Improvement at Baseline (End of █) and End of Treatment - Clinical Global Impression

Figure 14.2.7.1_AH1a Plot of Change from Week █ to Week █ in Clinician-completed Domain Specific Causes for Concern VAS: Myotonic Dystrophy

Figure 14.2.7.1_AH1b Plot of Change from Baseline to End of Treatment in Clinician-completed Domain Specific Causes for Concern VAS: Myotonic Dystrophy

Figure 14.2.7.1_AH1c Scatter Plot of Clinician-completed Domain Specific Causes for Concern VAS: Myotonic Dystrophy at Week █

Figure 14.2.9.1_AH1a Plot of Change from Week █ to Week █ in Caregiver Top Three Concerns VAS Total Score (cm)

Figure 14.2.9.1_AH1b Plot of Change from Baseline to End of Treatment in Caregiver Top Three Concerns VAS Total Score (cm)

Figure 14.2.9.1_AH1c Scatter Plot of Caregiver Top Three Concerns VAS Total Score (cm) at Week █

Figure 14.2.10.1_AH1a Bar Chart of OSU Global Improvement Scale for Autism over Time – Mean Score +/- Standard Deviation

Figure 14.2.10.1_AH1b Bar Chart of Percentage of Subjects with Improvement at Baseline (End of █) and End of Treatment – OSU Global Improvement Scale for Autism

Figure 14.2.11.1_AH1a Bar Chart of Peabody Picture Vocabulary Test over Time – Mean Value +/- Standard Deviation

Figure 14.2.11.1_AH1b Scatter Plot of Peabody Picture Vocabulary Test at Week -2

Figure 14.2.12.1_AH1a Bar Chart of DXA Scan (Body Composition - Lean Muscle Mass) over Time – Mean Value +/- Standard Deviation

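### Adverse events in the short placebo run-in and the 12-week active period are reported only as counts and percentages of subjects, with no time denominator, so the two sets of figures are not comparable as they stand

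*SAP*

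**What the plan says.** SAP 7.1 classifies adverse events by onset relative to the first active dose. The run-in definition reads: "A NTEAE is defined as an AE that started on or after the administration of placebo treatment". That window closes when tideglusib is first given. Anything starting from the first active dose is a TEAE. TEAEs are divided into a treatment-period group, which closes 2 days after active treatment stops, and a post-treatment group, and are also shown combined.

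Both NTEAEs and TEAEs are summarised as numbers of events and numbers of subjects, and then as percentages of subjects by system organ class and preferred term. Under SAP 1, adverse event percentages use the analysis set as denominator. No rate per unit of time is specified, and no window on active treatment is matched to the run-in.

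Two related items are already planned. SAP 4.4 summarises "the number of days of exposure to the active treatment derived from the subject diary card data", but does not connect it to the adverse event tables, and it covers tideglusib only. SAP 7.1 lists each event with its onset relative to the first active dose.

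Protocol 8.1 makes adverse event incidence the primary endpoint, counted from baseline to the follow-up visit. Protocol 7.1 explains that the run-in is there for analysis.

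**The concern.** The chance that a subject has at least one event grows with the time observed. If one window is several times longer than the other, its percentage will be higher even when the drug does nothing.

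The trial has no concurrent placebo group, so the run-in is the only placebo experience available. A reader who wants to know whether an event is more frequent on tideglusib will look from the NTEAE table to the TEAE table. SAP Appendix 1 encourages this: those two are the only summary tables in the planned Cohort 1 package. What is at stake is a false impression of harm for individual event terms, produced by duration alone.

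**Working it through.** The documents give no adverse event rate, power or sample size calculation, so there is no figure of the plan's own to reproduce. The check asks what an inert drug would show.

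**Inputs**

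- Active period: 12 weeks, or 84 days (Protocol 8.3). The treatment-period TEAE window can run to about 86 days (SAP 7.1).
- Run-in: redacted in the design text and taken here as 14 days. SAP Appendix 2 has an output titled "Scatter Plot of Peabody Picture Vocabulary Test at Week -2". Protocol 10.2.12 schedules that test only at run-in, baseline and end of treatment, "to compare scores prior and after single-blind placebo and single-blind tideglusib respectively". Week -2 must therefore be the run-in visit.
- Cross-check from supply: Cohort 2 gets "1 x carton containing 18 sachets" for the run-in (Protocol 9.1.2), taken once daily, which caps it at 18 days. "An additional 2 sachets of medication are also included in the carton" (Protocol 9.1), leaving 18 - 2 = 16 daily doses. That fits 14 days plus a visit window; the window is an assumption.
- Subjects: 8 per dose group (SAP 2.4).
- Background event rate: not given, so varied.

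**Formula**

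With one constant rate in both windows and a 2-week risk p, the 12-week risk is 1 - (1 - p)^(84/14) = 1 - (1 - p)^6. The apparent ratio is that risk divided by p.

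| 2-week risk | 12-week risk | Ratio |
|---|---|---|
| 2% | 11.4% | 5.7 |
| 5% | 26.5% | 5.3 |
| 10% | 46.9% | 4.7 |
| 12.5% (1 of 8) | 55.1% | 4.4 |
| 20% | 73.8% | 3.7 |
| 25% (2 of 8) | 82.2% | 3.3 |
| 30% | 88.2% | 2.9 |
| 50% | 98.4% | 2.0 |
| 60% | 99.6% | 1.7 |

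For example, 1 - 0.875^6 = 0.551, and 0.551/0.125 = 4.4. The ratio cannot exceed 6 (84/14), and it shrinks as the 12-week risk approaches 100%.

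**Sensitivity**

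- An 18-day run-in gives a window ratio of 84/18 = 4.7. The apparent ratio is then 4.5 at a run-in risk of 2%, 3.9 at 10% and 2.7 at 30%.
- An 86-day active window gives 86/14 = 6.1, and 4.8 rather than 4.7 at 10%.
- The combined TEAE rows also include follow-up, whose length is redacted. If it is 2 to 10 weeks (assumed), the ratio at a 10% 2-week risk is 5.2 to 6.9.

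**In a cohort of 8**

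In 200,000 simulated cohorts on an inert drug, more subjects had an event in the active period than in the run-in in 93% of cohorts at a 10% 2-week risk and 98% at 20%. At least twice as many did so in 88% and 89%.

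**What a time denominator does**

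A 10% 2-week risk is -ln(0.9)/2 = 0.053 events per subject-week in either window. Planned exposure per cohort is 8 x 2 = 16 subject-weeks in the run-in and 8 x 12 = 96 on active treatment, so about 0.8 and 5.1 events are expected. The counts differ 6-fold, but the rates are equal.

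Precision is poor. One event in 16 subject-weeks is 0.063 per week, with exact Poisson 95% limits of 0.0253/16 = 0.002 and 5.572/16 = 0.35.

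**The case against.** The strongest reply is that the SAP makes no such comparison. NTEAEs and TEAEs are in separate tables with no ratio, difference or test between them. This stands: the distortion arises only when the two are read together.

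A reader might go further and infer that the primary safety result cannot be interpreted. The documents do not support that. The primary window opens at baseline, so the run-in is outside it, and TEAE incidence by dose over a planned 12 weeks is a sound descriptive result. Nor is the run-in the only comparator: the two dose groups have the same planned duration, although they are not randomised. It is the only placebo reference.

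A reader might also take Protocol 11.4 as planning a run-in contrast for adverse events. Its statement about run-in change concerns laboratory, vital sign and ECG values. For adverse events it asks only for frequencies and percentages.

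A third inference is that early stopping makes a poorly tolerated dose look better. The documents give no basis for sizing this. A subject who stops because of a TEAE is already counted as having one, and appears again in the discontinuation rows.

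The SAP also has partial safeguards: event counts, the split between treatment and post-treatment TEAEs, summaries by relationship, and listed onset times. With 16 subjects, a determined reader could build the matched window from the listing. That reduces the harm, but leaves the work to the reader.

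Finally, the added rates will be very imprecise. This is true, and showing it is useful, because it tells the reader how little the run-in can say.

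**Conclusion.** The point holds as a gap in presentation, not as an error in the primary analysis. Adverse event percentages from two windows that differ about 6-fold in length are reported with nothing to put them on a common footing, and the shorter window is the only placebo experience.

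For an inert drug the apparent excess is about 5- to 6-fold for terms with a 2-week risk of 5% or less, 3- to 5-fold at 10% to 25%, and 2-fold or less from 50%. Individual preferred terms are thus the most exposed; a row for any adverse event may show little excess if nearly every subject has one.

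Three assumptions carry this. The event rate is roughly constant; events clustered soon after the first placebo dose would shrink the ratio. The run-in is about 2 weeks, which is inferred, though the conclusion survives at 18 days. The background rate is unknown, which is why a range is given.

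Two SAP rules can add to the imbalance, by an amount that cannot be sized here. Unclear onset dates default to treatment-emergent. Safety summaries include only subjects who received active drug, so events in subjects who leave during the run-in drop out of the tables.

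**What to change.** In SAP 7.1:

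- Add a time-matched row or table. It should give the percentage of subjects with an event starting in the run-in beside the percentage with a TEAE starting within an equal number of days from the first active dose. The onset time already derived for the listing is enough to select these TEAEs.
- Add first-event rates per subject-week, with each subject's time censored at the first event, and exact 95% confidence intervals, for the run-in and each dose group. Using first events avoids treating repeat events in one subject as independent.
- State in the text and as a table footnote that the full-period NTEAE and TEAE percentages cover unequal durations.

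The cost is one or two tables and two small derivations: run-in exposure days, which SAP 4.4 does not provide but which follow from the diary dose dates (Protocol 10.3.1), and time to first event. No new data or visits are needed. The run-in rates will have very wide intervals at about 16 subject-weeks per cohort, and the time-matched row says nothing about later-onset events, so the full TEAE tables must stay.
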